7. PLANNED ANALYSIS

For End-Of-Text (EoT) tables, the set of summary statistics is: N / Mean / SD / Min / Q1 (lower quartile) / Median / Q3 (upper quartile) / Max.

Tabulations of frequencies for categorical data will include all possible categories and will display the number of observations in a category as well as the percentage (%) relative to the respective treatment group (unless otherwise specified, all patients in the respective patient set whether they have non-missing values or not). Percentages will be rounded to one decimal place. The category missing will be displayed only if there are actually missing values.

7.1 DEMOGRAPHIC AND OTHER BASELINE CHARACTERISTICS

Only descriptive statistics are planned for this section of the report.

7.2 CONCOMITANT DISEASES AND MEDICATION

Only descriptive statistics are planned for this section of the report.

7.3 TREATMENT COMPLIANCE

Only descriptive statistics are planned for this section of the report.

Compliance will be calculated for subjects having attended the visit. A subject is considered having attended the visit if the indicated visit is captured in the eCRF database. In particular, if a subject attended the visit, but is not treated at the visit, the compliance of this visit is considered as 0%.

Compliance with trial medication will be based on the drug infusion/administered eCRF data and calculated as amount of drug infused/administered divided by the amount of drug to be infused/administered expressed as a percentage, see calculations below.

"Per Visit" Compliance to trial medication will be calculated as follows:

 $\frac{\text{(Amount of drug infused/administered at Visit X(n))}}{\text{(Amount of drug planned to be infused/administered at Visit X(n))}} \times 100$

Overall Compliance for first treatment cycle will be calculated as mean of "per visit" compliance at visit Day 1, Day 8 and Day 15.

Overall Compliance for second treatment cycle onwards (from Day 22 onwards) will be calculated as mean of "per visit" compliance at each visit within the cycle. Overall Compliance to trial medication will be calculated as mean of the "per visit" compliance.

The compliance will be based on the total volume infused in mL (eCRF data) compared to total volume prepared (eCRF data).

7.4 PRIMARY ENDPOINT(S)

The primary endpoint is to assess the MTD based on the number of patients presenting DLTs during the MTD evaluation period. The primary analysis is for the determination of the MTD. The purpose of this analysis is to summarize and document the data that led to the selection of the MTD. Therefore, an overall summary of DLTs (see CTP section 5.3.1 for the definition of DLTs) which occurred during the MTD evaluation period will be provided for each dose cohort from the dose finding cohort treated set. Patients, if any, who did not complete the MTD evaluation period for reasons other than DLT will be excluded from the analysis of the primary endpoint.

A summary of the number of patients with DLTs overall in any course will be also given by initial treatment and displayed in a similar format to the summary of DLTs occurring in the MTD evaluation period.

The analysis of the MTD is based on a Bayesian logistic regression model (BLRM) guided by the escalation with overdose control principle. The MTD is defined as the highest dose for a given schedule that is expected to cause less than 25% risk of the true DLT rate being above or equal to 33% during the MTD evaluation period. Estimation of the MTD during the dose escalation phase of the study will be based upon the estimation of the posterior probability of the incidence of DLT in toxicity categories during the MTD evaluation period for all evaluable patients. The model to be used is specified in CTP section 7.

The posterior probabilities that the toxicity rates of each dose level fall into the categories specified in CTP section 7 will be displayed.

7.5 SECONDARY ENDPOINT(S)

7.5.1 Key secondary endpoint(s)

This section is not applicable as no key secondary endpoint has been specified in the protocol.

7.5.2 (Other) Secondary endpoint(s)

Drug related AEs leading to treatment discontinuation or dose reduction will be analysed as part of safety analysis as described in section 7.8.1.

TSAP for BI Trial No: 1336.6 Page 15 of 23
Proprietary confidential information © 2017 Boehringer Ingelheim International GmbH or one or more of its affiliated companies

TSAP for BI Trial No: 1336.6

Proprietary confidential information © 2017 Boehringer Ingelheim International GmbH or one or more of its affiliated companies

7.7 EXTENT OF EXPOSURE

Treatment exposure will be primarily summarized by the total on-treatment time and has been defined in section 5.4 of this TSAP.

Treatment interruptions before permanent discontinuation will not be excluded. Summary statistics for treatment time by each dose level and the dosage of BI 836880 over time will also be provided.

7.8 SAFETY ANALYSIS

All safety analyses will be performed on the treated set.

7.8.1 Adverse events

The analyses of adverse events (AE) will be descriptive in nature. All analyses of AEs will be based on the number of patients with AEs and not on the number of AEs. Two analyses will be performed. The first analysis of safety will be performed for the first part of the trial (determination of the MTD, first cycle only (3-week treatment), treatment regimen = initial dose at the start of the treatment, treated set). This descriptive analysis will evaluate the MTD for the monotherapy of BI 836880. The second analysis will be performed with respect to all cycles and will act as a support for the determination of the MTD (treated set).

For analysis of duration, severity etc. of multiple AE occurrences, data on the case report form (CRF) will be collapsed into AE episodes provided that all of the following applies:

- The same MedDRA lowest level term was reported for the occurrences.
- The occurrences were time-overlapping or time-adjacent (time-adjacency of two occurrences is given if the second occurrence started on the same day or on the day after the end of the first occurrence).
- Treatment did not change between the onset of the occurrences or treatment changed between the onsets of the occurrences, but no deterioration was observed for the later occurrence.

For further details on summarization of AE data, please refer to the guideline 'Handling and summarization of adverse event data for clinical trial reports and integrated summaries' (5).

For patients treated with the test drug, that means that all adverse events occurring between first drug intake and 42 days after last drug intake or death, whichever occurs first, will be assigned to the on-treatment period. All adverse events occurring before any study drug intake will be assigned to 'screening' and all adverse events occurring after last study drug intake + 42 days will be assigned to 'post-study' (for listings only). For details on the treatment definition, see section 6.1.

An overall summary of adverse events will be presented. This summary will exclude the rows 'Severe AEs', 'Significant AEs' and 'Other significant AEs' but will include additional rows for 'AEs leading to dose reduction', 'AEs leading to death' and 'AEs by highest Common Terminology Criteria (CTC) grade'.

The frequency of patients with adverse events will be summarised by highest CTC grade (grades 1, 2, 3, 4, 5 and all grades), treatment, primary system organ class and preferred term for each of the following AE tables as well as relatedness of AEs to treatment and seriousness:

- All AEs
- Drug-related AEs
- AEs leading to dose reduction
- AEs leading to treatment discontinuation

- Drug-related AEs leading to treatment discontinuation
- Drug related AEs leading to dose reduction
- Drug related AEs leading to treatment discontinuation or dose reduction
- AEs leading to death
- Serious AEs
- Drug related serious AEs
- Non-serious AE with higher than 5% occurrence rate
- DLTs

All tables will be sorted by system organ classes (SOC) according to the standard sort order specified by the European Medicines Agency (EMA). Preferred terms (PTs) will be sorted by frequency (within SOC).

The above tables will be repeated with the project defined grouping of AE terms. Details of the project defined groupings are defined in the technical TSAP. In these tables the grouped AEs will replace the original PTs for all AEs that are included within the grouped term. The grouped AE categories will then be tabulated along with all remaining MedDRA PTs, sorted by descending frequency.

A reference table presenting the entire project defined groupings and MedDRA PTs within each grouping will also be produced.

Additional AE tables will be produced for AEs of special interest (hepatic injury as defined in CTP section 5.3.8.1 and dose limiting toxicities as defined by 5.3.1), providing further details on highest CTC grade, action taken with study drug and time to first onset of AE.

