3.3.4 Removal of patients from therapy or assessments

3.3.4.1 Removal of individual patients

An individual patient is to be withdrawn from trial treatment if:

- The patient withdraws consent for study treatment or study participation, without the need to justify the decision.
- Requiring concomitant drugs that interfere with the investigational product or other trial medication (see Section 4.2.2) or patient who requires concomitant drugs, which in the opinion of the investigator may interfere with the investigational drug.
- The patient can no longer be treated with trial medication for other medical reasons (such as surgery, adverse events, other diseases, or pregnancy).
- The patient is no longer able to complete trial visit or trial-required procedures.
- A DLT occurs which does not recover to a degree that allows continuation of treatment (see Section 4.1.4) for re-treatment criteria and dose reduction scheme)
- Progressive disease (except in cases with intra-patient dose escalation, (see Section 4.1.3) or start of any new anti-cancer therapy.

A patient can have withdrawn from the trial after discussion between the Investigator and the Sponsor if eligibility criteria are violated and/or the patient fails to comply with the protocol.

All withdrawals will be documented and the reason for withdrawal recorded and discussed, as necessary, in the final Clinical Trial Report (CTR). As soon as a patient is withdrawn from the study treatment, the end of treatment visit (EoT) has to be performed if feasible. Every effort should be made to follow-up with patients in case an adverse event is still ongoing at the time of withdrawal. If a patient is withdrawn from the trial due to consent withdrawal, no further visit will be completed.

Patients who have not completed first course of BI 836880 treatment (3 weeks) for any other reason than BI 836880 related toxicities will be considered not evaluable for MTD evaluation and should be replaced.

Patient who prematurely discontinue study drug for above mentioned reasons or any other reason, should have additional follow up visits until progression, lost to follow up, treatment with another anti-cancer treatment, death and /or end of the trial whichever comes first.

Trial Protocol Page 28 of 99

Proprietary confidential information © 2019 Boehringer Ingelheim International GmbH or one or more of its affiliated companies

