5.3.6.2 Adverse event collection and reporting

AE Collection

The Investigator shall maintain and keep detailed records of all AEs in their files. The following must be collected and documented on the appropriate CRF(s) by the Investigator:

- From signing the informed consent onwards until the end of treatment (including the Residual Effect Period, REP): all AEs (non-serious and serious) and all AESIs.

- After the end of treatment (including the REP) until the individual patient's end of trial: all related SAEs and all related AESIs.
- After the individual patient's end of the trial: the Investigator does not need to actively monitor the patient for AEs but should only report relevant SAEs and relevant AESIs of which the Investigator may become aware of.

The rules for Adverse Event Reporting exemptions still apply.

[figure not shown]

Figure 5.3.6.2: 1AE collection

The REP is defined as 42 days after the last trial medication application. All AEs which occurred through the treatment phase and throughout the REP will be considered as on treatment (please see Section 7.3.4). Events which occurred after the REP will be considered as post treatment events.

AE reporting to sponsor and timelines

The Investigator must report SAEs, AESIs, and non-serious AEs which are relevant for the reported SAE or AESI, on the BI SAE form via fax immediately (within 24 hours) to the Sponsor's unique entry point (country specific contact details will be provided in the ISF). The same timeline applies if follow-up information becomes available. In specific occasions the Investigator could inform the sponsor upfront via telephone. This does not replace the requirement to complete and fax the BI SAE form.

With receipt of any further information to these events, a follow-up SAE form has to be provided. For follow-up information the same rules and timeline apply as for initial information.

Information required

For each AE, the Investigator should provide the information requested on the appropriate CRF pages and the BI SAE form. The Investigator should determine the causal relationship to the trial medication.

The following should also be recorded as an (S)AE in the CRF and SAE form (if applicable):

- Worsening of the underlying disease or of other pre-existing conditions. The rules for Adverse Event Reporting exemptions still apply

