6.2.3.2 Residual effect period (REP)

The REP is defined in Section 5.3.6.2. The End of the Residual period visit (EoR) should not be performed earlier than 42 days after permanent discontinuation of the study drug. The information collected at this visit should include all new AEs that occurred after EOT and a follow-up of adverse events ongoing at EOT. Any subsequent anti-cancer therapy administered between EOT and EoR should be reported.

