7.3.4 Safety analyses

All patients of the treated set will be included in the safety analyses. Two analyses will be performed. The first analysis of safety will be performed for the first part of the trial

Page 60 of 99

Proprietary confidential information © 2019 Boehringer Ingelheim International GmbH or one or more of its affiliated companies

(determination of the MTD, first course only, treatment regimen = initial dose at the start of the treatment, treated set). This descriptive analysis will evaluate the MTD for the monotherapy of BI 836880. The second analysis will be performed with respect to all courses and will act as a support for the determination of the MTD (treated set).

Events that started between the first administration of the treatment until 6 weeks (42 days) after the last administration of treatment will be considered as having occurred on treatment. Events that started after 42 days since last administration of treatment will be considered as having occurred post-treatment and will be presented separately.

Adverse events will be graded according to CTCAE Version 4.03 (R12-2532) and reported according to BI standards. Frequency, severity, and causal relationship of adverse events will be tabulated by system organ class and preferred term after coding according to the current version of the Medical Dictionary for Drug Regulatory Activities (MedDRA).

Serious adverse events will be tabulated. In addition, events leading to dose reduction or treatment discontinuation will be examined, but may not be reported as individual tables, depending upon the extent of overlap. Descriptive statistics will be used to describe changes in laboratory tests over time. In addition, all abnormalities of potential clinical significance will be reported. In general, potential clinical significance is defined as at least CTCAE Grade 2 and an increase in CTCAE classification from baseline. The incidence and severity of the more important adverse events (as determined from the analyses above) will be correlated descriptively with pharmacokinetic data, if possible.

Adverse events will be coded using the Medical Dictionary for Regulatory Activities (MedDRA) coding dictionary. Standard BI summary tables and listings will be produced. All adverse events with an onset between start of treatment and end of the residual effect period (REP), a period of 42 days after the last dose of trial medication, will be assigned to the treatment period for evaluation.

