6. GENERAL ANALYSIS DEFINITIONS

6.1 TREATMENT(S)

The starting dose of the study is BI 836880 40 mg every week, and dose escalation decision will be made by Data Safety Board (DSB).

The following treatment period will be defined:

- Screening: from the date of informed consent to the date of first study medication intake -1 day.
- On-treatment: from the date of first intake of study drug to the date of last study drug administration + 42 days, i.e., actual on-treatment period + residual effect period (REP).
- Post-study: from the last day of on-treatment period + 1 day onwards

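### The 42-day on-treatment window has no cut-off or flag at the start of new anti-cancer therapy, so the all-causality, all-cycle AE tables can include toxicity of the next treatment

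*SAP*

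**What the plan says.** The window is defined consistently in both documents.

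- SAP 6.1: "On-treatment: from the date of first intake of study drug to the date of last study drug administration + 42 days".
- SAP 7.8.1, on which AEs count as on-treatment: "all adverse events occurring between first drug intake and 42 days after last drug intake or death, whichever occurs first, will be assigned".
- Protocol 7.3.4 treats as on treatment "Events that started between the first administration of the treatment until 6 weeks (42 days) after the last administration of treatment".
- Protocol 5.3.6.2 collects AEs over the same span: "until the end of treatment (including the Residual Effect Period, REP): all AEs (non-serious and serious) and all AESIs".

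The protocol foresees that another treatment may begin before the window closes. Withdrawal from trial treatment follows progression or "start of any new anti-cancer therapy" (Protocol 3.3.4.1). For the residual effect period, Protocol 6.2.3.2 says: "Any subsequent anti-cancer therapy administered between EOT and EoR should be reported".

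On the use of the resulting tables, SAP 7.8.1 says: "The second analysis will be performed with respect to all cycles and will act as a support for the determination of the MTD". Protocol 3.1 adds that the RP2D is confirmed on all available safety data, over every course and dose level.

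**The concern.** A patient can stop BI 836880, start another anti-cancer drug two or three weeks later, and have a serious or high-grade event on that drug before day 42. Under the rule as written, the event counts as on-treatment and is shown under the patient's BI 836880 dose.

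The tables count patients by highest CTC grade, so a single such event can set a patient's worst grade. Cohorts may be as small as two or three patients (Protocol 3.1), and these tables are named as support for the MTD. A reader of the report could not tell which events arose under the next treatment.

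Elsewhere the protocol does treat new therapy as an end point. Follow-up visits for progression stop at the start of another anti-cancer treatment (Protocol 6.2.3.3), and so does the tumour assessment schedule (Protocol 5.2). AE assignment has no matching rule.

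**Working it through.** The plan states no figure on this point, so there is none to reproduce. The only stated arithmetic, 6 weeks = 42 days in Protocol 7.3.4, is correct.

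**Step 1: which outputs are exposed.** SAP 7.8.1 lists 12 AE tables.

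| Group | Number | Exposed? |
|---|---|---|
| Restricted to drug-related events | 5 | Only if causality is misjudged |
| DLTs (drug-related by definition, Protocol 5.3) | 1 | Only if causality is misjudged |
| AEs leading to dose reduction; AEs leading to discontinuation | 2 | No: an event starting after the last dose cannot lead to either |
| All AEs; AEs leading to death; serious AEs; non-serious AEs above 5% | 4 | Yes |

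Check: 5 + 1 + 2 + 4 = 12. The matching rows of the overall summary and the repeats with grouped terms are exposed in the same way. So is the hepatic-injury AESI table, because Protocol 5.3.6.1 defines that AESI by laboratory thresholds with no relatedness condition. Its exposure depends on a late EOT sample or an unscheduled one (step 2).

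**Step 2: laboratory data.** The flow charts schedule safety laboratory tests at screening, Days 1, 8 and 15, and EOT. The EoR and FU columns are blank. EOT is due within 21 days of the last administration, so no scheduled sample falls in the second half of the 42 days. The scheduled laboratory tables are essentially unaffected.

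**Step 3: the room for overlap.** With every weekly infusion given, the last infusion falls on day 21 × (courses − 1) + 15, and the window ends 42 days later. For the last two columns, new therapy is assumed to start 28 or 14 days after the last infusion, which leaves 14 or 28 days of overlap.

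| Full courses | Last infusion | Window end | 42-day tail as share of window | 14 days of overlap | 28 days of overlap |
|---|---|---|---|---|---|
| 1 | day 15 | day 57 | 42/57 = 74% | 25% | 49% |
| 2 | day 36 | day 78 | 42/78 = 54% | 18% | 36% |
| 4 | day 78 | day 120 | 42/120 = 35% | 12% | 23% |
| 8 | day 162 | day 204 | 42/204 = 21% | 7% | 14% |

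These shares show opportunity only. The tables count patients, not days, so a share of days is not a bias in any table. The tail share would be the same if nobody switched.

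**Step 4: patients affected, by assumption.** The documents give no switching rate. Take about 25 treated patients (Protocol 3.3). Assume that a proportion p starts new therapy inside the window and that a proportion q of those has a new AE from it. Expected number affected = 25 × p × q.

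- Low: p = 10%, q = 50%: 25 × 0.10 × 0.50 = 1.25 patients.
- High: p = 50%, q = 80%: 25 × 0.50 × 0.80 = 10 patients.

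For six independent patients at one dose, the chance of at least one affected is 1 − (1 − pq)^6. This is 1 − 0.95^6 = 0.27 at the low end and 1 − 0.60^6 = 0.95 at the high end. The range is too wide to be an estimate. It shows only that the effect could be negligible or visible.

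**Step 5: weight of one patient.** One affected patient is 1/2 = 50% of a cohort of two and 1/3 = 33% of a cohort of three.

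**The case against.** The strongest reply is that little of importance is touched and that a fixed window is sound.

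- **The MTD.** A reader might infer that the MTD itself is contaminated. The documents do not support that. The MTD comes from the Bayesian model on drug-related DLTs within three weeks of the first dose (SAP 5.1 and 7.4, Protocol 5.3), and the all-cycle tables only support it. The secondary endpoint is also limited to drug-related events tied to dose reduction or discontinuation. This part of the reply stands.
- **Laboratory shift tables.** A reader might extend the point to these. Step 2 shows why that largely fails.
- **Dose dependence.** A reader might infer that short-stay doses are hit harder. No section links dose to time on drug or to switching, so neither unevenness nor its direction can be claimed.
- **Counterparts and exemptions.** All AEs and serious AEs each have a drug-related counterpart, and death from progression is exempt from SAE reporting (Protocol 5.3.6.2). Both limit the damage. Neither identifies the all-causality events that began after a switch.
- **Late effects.** A fixed 42-day window keeps late BI 836880 events, which truncation alone would lose. This is a good reason to keep the 42-day tables and not let truncated ones replace them. It is no reason against a flag and a sensitivity repeat.
- **Unseen rules.** SAP 7.8.1 refers to an internal AE-handling guideline that is not available, and parts of the SAP are missing from the public text, so a rule may exist there. But SAP 7.8.1 states the assignment outright with death as the only early end, and any further cut-off belongs beside it.

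**Conclusion.** The gap is real and narrow. As written, the all-causality, all-cycle tables (all AEs, serious AEs, AEs leading to death, non-serious AEs above 5%, and hepatic-injury AESIs) can include events caused by the next anti-cancer therapy, with nothing to mark them. The frequency cannot be derived. The 1.25 to 10 patients out of 25 rest entirely on assumed switching and event rates. What does follow from the documents is that the overlap is foreseen, that one patient carries much weight in a cohort of two or three, and that these tables are named as support for the MTD and are part of the safety data behind the RP2D.

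The formal MTD and the scheduled laboratory data are essentially unaffected, as are the drug-related tables to the extent that causality is judged correctly. This is a low-cost improvement to the reporting, not a flaw in the dose-finding.

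**What to change.** Keep the 42-day tables as the main presentation. In SAP 7.8.1:

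1. Flag in the listings every AE that starts on or after the start of new anti-cancer therapy.
2. Pre-specify a sensitivity repeat of the exposed tables (all AEs by highest CTC grade, serious AEs, AEs leading to death, non-serious AEs above 5%, hepatic-injury AESIs). End the window at the earlier of last dose + 42 days and the day before new therapy starts.
3. Show the repeat beside the full-window tables in the analysis that supports the MTD.

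Also confirm that the start date of subsequent therapy is captured. Protocol 6.2.3.2 asks for therapy between EOT and EoR to be reported, but it does not mention a start date and does not cover therapy begun before EOT. Protocol 4.2 describes the recording of concomitant therapy in terms of non-oncological treatment, so it does not clearly fill that gap.

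The cost is SAP wording and a few extra tables, plus one eCRF check. The small downside is that late BI 836880 effects after a switch appear only in the full-window tables, which are kept.

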All treated patients will be included in the safety analysis. In general, safety analyses will be descriptive in nature and will be based on BI standards. No hypothesis testing is planned.

Statistical analysis and reporting of adverse events will concentrate on treatment-emergent adverse events. To this end, all adverse events occurring between start of treatment and end of the residual effect period will be considered 'treatment-emergent'. The residual effect period is defined as 42 days after the last trial medication application. Adverse events that start before first drug intake and deteriorate under treatment will also be considered as 'treatment-emergent'.

Frequency, severity, and causal relationship of adverse events will be tabulated by system organ class and preferred term after coding according to the current version of the Medical Dictionary for Drug Regulatory Activities (MedDRA).

Laboratory data will be analysed both quantitatively as well as qualitatively. The latter will be done via comparison of laboratory data to their reference ranges. Values outside the

Trial Protocol

Page 61 of 99

Proprietary confidential information © 2019 Boehringer Ingelheim International GmbH or one or more of its affiliated companies

reference range as well as values defined as clinically relevant will be highlighted in the listings. Treatment groups will be compared descriptively with regard to distribution parameters as well as with regard to frequency and percentage of patients with abnormal values or clinically relevant abnormal values.

Vital signs, physical examinations, or other safety-relevant data observed at screening, baseline, during the course of the trial and at the end-of-trial evaluation will be assessed with regard to possible changes compared to findings before start of treatment.

Boehringer Ingelheim BI Trial No.: 1336.6 c03124055-06

Trial Protocol

Page 62 of 99

13 Mar 2019

Proprietary confidential information © 2019 Boehringer Ingelheim International GmbH or one or more of its affiliated companies

A055-06 Trial Protocol Page 63 of 99

Proprietary confidential information © 2019 Boehringer Ingelheim International GmbH or one or more of its affiliated companies

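### The SAP's period rule for adverse events omits the protocol's provision for pre-dose events that worsen on drug, so worsening held on a single record would be classed as screening

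*SAP*

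**What the plan says.** Protocol section 7.3.4 defines on-treatment events by start date, from the first administration to 42 days after the last. Further on it adds a second route: "Adverse events that start before first drug intake and deteriorate under treatment will also be considered as" treatment-emergent.

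SAP section 6.1 defines the periods by calendar date alone: "Screening: from the date of informed consent to the date of first study medication intake -1 day", followed by an on-treatment period running to the last administration plus 42 days. SAP section 7.8.1 applies these periods to adverse events. The on-treatment period takes "all adverse events occurring between first drug intake and 42 days after last drug intake or death, whichever occurs first". For earlier events the rule is: "All adverse events occurring before any study drug intake will be assigned to" screening. Neither section makes an exception for deterioration.

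The same SAP section also says when separate CRF occurrences are merged into one episode. Where treatment changed between two onsets, they are merged only if "treatment changed between the onsets of the occurrences, but no deterioration was observed for the later occurrence".

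SAP section 3 says the plan is based on protocol section 7. SAP section 4, on changes to the planned analysis, lists only the reporting of biomarkers.

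**The concern.** The protocol classifies by onset and by deterioration; the SAP classifies by period only. Adverse events are collected from consent (protocol 5.3.6.2), which can be up to 21 days before dosing, in patients with advanced cancer. Some events will therefore begin before the first infusion and continue through it. Protocol section 2.3 expects fatigue, hypertension and proteinuria among the drug's effects, and each of these can be present at a low grade before dosing.

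The SAP's tables report the highest CTC grade per patient. If a low-grade screening event rises to a higher grade on drug and stays in the screening period, that higher grade is missing from the on-treatment tables. The secondary endpoint is exposed in the same way, because SAP section 7.5.2 sends it to section 7.8.1 for analysis. Under the SAP's rule such an error could only lower the on-treatment count.

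**Working it through.** There is no sample size, power or error-rate figure to reproduce. The check is a comparison of the two texts for each way in which worsening can be recorded.

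1. **Worsening entered as a second CRF record, with onset after the first infusion.** Protocol: treatment-emergent. SAP: the two records straddle a treatment change and the later one deteriorated, so the collapsing rule does not merge them. The second record keeps its own on-treatment onset and is counted. The documents agree.

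2. **Worsening held on one record, with onset before the first infusion and the higher grade reached afterwards.** Protocol: treatment-emergent, by the deterioration provision. SAP: there is only one occurrence, so the collapsing rule has nothing to compare. With a pre-dose onset, the record goes to screening. The documents conflict.

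3. **No worsening after the first infusion.** Neither document counts the event as arising on treatment. They agree.

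The conflict is therefore confined to case 2.

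The result depends on reading the SAP's word for when an event occurs as its onset. On the other reading (presence at any time), an event that spans the first infusion satisfies both the screening sentence and the on-treatment sentence, and the SAP gives no rule for choosing between them. Case 2 is unresolved on that reading and contrary to the protocol on the first.

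Other displays recover part of what case 2 would lose:

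- SAP section 7.8.2 tabulates CTC-grade transitions from baseline to the worst value on treatment for laboratory parameters, and names urine protein as a focus.
- Vital signs are summarised descriptively under SAP section 7.8.3.
- The plan describes no comparable display for symptoms such as fatigue, or for the secondary endpoint.

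Size per affected patient, using cohort sizes from the protocol:

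- minimum cohort of 2 (section 3.1): 1/2 = 50 percentage points;
- 6 patients at the MTD (section 7.1): 1/6 = 17 percentage points.

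These figures give the weight of one patient in one table row. They are not an estimate of expected bias.

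**The case against.** The strongest reply is that the SAP repeats one protocol rule without repealing the other. The protocol itself holds an onset rule beside the deterioration provision. The SAP assumes familiarity with the protocol, and the absence of a declared change fits the provision still standing. The SAP also defers further handling: "For further details on summarization of AE data, please refer to the guideline", naming a sponsor document that is not available here and could settle the point. In addition, protocol section 5.3.6.2 asks for the following to be recorded as an (S)AE: "Worsening of the underlying disease or of other pre-existing conditions". It treats abnormalities present before inclusion as baseline conditions, so much of the background burden of advanced cancer should produce a new record when it worsens.

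Much of this stands. It narrows the problem to events that arise between consent and first dose, worsen on drug and stay on one record. It does not remove the conflict. The SAP is the text that will be programmed, and its screening sentence has no exception. The protocol asks for worsening to be recorded but does not say that a new record is needed, and the documents do not show how the eCRF holds a grade change within an ongoing event.

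A reader might infer three stronger conclusions, none of which the documents support:

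- **That every pre-dose event that worsens is lost.** The collapsing rule keeps a deteriorated second record as a separate on-treatment episode.
- **That dose-limiting toxicities would drop out and the MTD would shift.** First-course DLTs are assessed patient by patient (protocol 7.3.1) and summarised in their own right (SAP 7.4), with no filter on the start date of an earlier low-grade event. DLT events at any time during the repeated courses or follow-up must also be reported as events of special interest (protocol 5.3.6.1).
- **That some percentage of the roughly 25 treated patients is affected.** The documents give nothing from which to derive one.

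**Conclusion.** The SAP and protocol disagree on how to classify a pre-dose event that deteriorates on treatment, and the SAP does not declare the difference. The disagreement takes effect only when the worsening sits on a single record with a pre-dose onset. The record would then be classed as screening and be absent from the on-treatment tables, including drug-related events leading to dose reduction or discontinuation.

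This rests on three assumptions: that occurrence in SAP 7.8.1 means onset, that the frequency tables are restricted to the on-treatment period, and that the unseen sponsor guideline does not restore the protocol's rule. How often the case arises is unknown. When it does, on-treatment toxicity is understated, and one patient weighs heavily in cohorts this small. No effect on the MTD determination has been shown. The point merits correction in the SAP but does not threaten the primary analysis.

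**What to change.** Add one sentence to SAP sections 6.1 and 7.8.1: an adverse event with onset before first intake, whose CTC grade increases between first intake and last intake plus 42 days, is assigned to the on-treatment period at the worsened grade and with the date of worsening, in line with protocol section 7.3.4.

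Also confirm in the SAP whether the eCRF requires a new record for each worsening. If it does, the sentence only documents what the collapsing rule already achieves. If it does not, query the date of worsening for ongoing events that began before the first infusion.

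Cost: one sentence, one derivation flag and possibly a few data queries. If the sponsor guideline already contains the rule, the sentence simply brings the SAP into line with the protocol.
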